Symptoms of abdominal pain associated with elevations of amylase and lipase, suggestive of pancreatitis, have been associated with the administration of atezolizumab. The differential diagnosis of acute abdominal pain should include pancreatitis. Appropriate workup should include an evaluation for ductal obstruction, as well as serum amylase and lipase tests. Management guidelines for pancreatic events, including pancreatitis, are provided in Table 8.

Table 8Management Guidelines for Pancreatic Events, Including
Pancreatitis

Event	Management
Amylase and/or lipase elevation, Grade 2	 Amylase and/or lipase > 1.5–2.0 × ULN: Continue atezolizumab. Monitor amylase and lipase weekly. For prolonged elevation (e.g., > 3 weeks), consider treatment with corticosteroids equivalent to 10 mg/day oral prednisone. Asymptomatic with amylase and/or lipase > 2.0–5.0 × ULN:
	Treat as a Grade 3 event.
Amylase and/or lipase elevation, Grade 3 or 4	 Withhold atezolizumab for up to 12 weeks after event onset.^a Refer patient to GI specialist. Monitor amylase and lipase every other day. If no improvement, consider treatment with corticosteroids equivalent to 1–2 mg/kg/day oral prednisone. If event resolves to Grade 1 or better, resume atezolizumab.^b If event does not resolve to Grade 1 or better while withholding atezolizumab, permanently discontinue atezolizumab and contact Medical Monitor.^c
	 For recurrent events, permanently discontinue atezolizumab and contact Medical Monitor.^c

GI = gastrointestinal.

- ^a Atezolizumab may be withheld for a longer period of time (i.e., > 12 weeks after event onset) to allow for corticosteroids (if initiated) to be reduced to the equivalent of ≤ 10 mg/day oral prednisone. The acceptable length of the extended period of time must be agreed upon by the investigator and the Medical Monitor.
- ^b If corticosteroids have been initiated, they must be tapered over ≥1 month to the equivalent of ≤10 mg/day oral prednisone before atezolizumab can be resumed.
- ^c Resumption of atezolizumab may be considered in patients who are deriving benefit and have fully recovered from the immune-mediated event. Patients can be re-challenged with atezolizumab only after approval has been documented by both the investigator (or an appropriate delegate) and the Medical Monitor.

Table 8Management Guidelines for Pancreatic Events, Including
Pancreatitis (cont.)

Event	Management
Immune-mediated pancreatitis, Grade 2 or 3	 Withhold atezolizumab for up to 12 weeks after event onset.^a Refer patient to GI specialist. Initiate treatment with corticosteroids equivalent to 1–2 mg/kg/day IV methylprednisolone and convert to 1–2 mg/kg/day oral prednisone or equivalent upon improvement. If event resolves to Grade 1 or better, resume atezolizumab.^b If event does not resolve to Grade 1 or better while withholding atezolizumab, permanently discontinue atezolizumab and contact Medical Monitor.^c For recurrent events, permanently discontinue atezolizumab and contact Medical Monitor.^c
Immune-mediated pancreatitis, Grade 4	 Permanently discontinue atezolizumab and contact Medical Monitor. ° Refer patient to GI specialist. Initiate treatment with corticosteroids equivalent to 1–2 mg/kg/day IV methylprednisolone and convert to 1–2 mg/kg/day oral prednisone or equivalent upon improvement. If event does not improve within 48 hours after initiating corticosteroids, consider adding an immunosuppressive agent. If event resolves to Grade 1 or better, taper corticosteroids over ≥ 1 month.

GI = gastrointestinal.

- ^a Atezolizumab may be withheld for a longer period of time (i.e., > 12 weeks after event onset) to allow for corticosteroids (if initiated) to be reduced to the equivalent of ≤ 10 mg/day oral prednisone. The acceptable length of the extended period of time must be agreed upon by the investigator and the Medical Monitor.
- ^b If corticosteroids have been initiated, they must be tapered over ≥1 month to the equivalent of ≤10 mg/day oral prednisone before atezolizumab can be resumed.
- ^c Resumption of atezolizumab may be considered in patients who are deriving benefit and have fully recovered from the immune-mediated event. Patients can be re-challenged with atezolizumab only after approval has been documented by both the investigator (or an appropriate delegate) and the Medical Monitor.

DERMATOLOGIC EVENTS

Treatment-emergent rash has been associated with atezolizumab. The majority of cases of rash were mild in severity and self limited, with or without pruritus. A dermatologist should evaluate persistent and/or severe rash or pruritus. A biopsy should be considered unless contraindicated. Management guidelines for dermatologic events are provided in Table 9.

Event	Management
Dermatologic event, Grade 1	 Continue atezolizumab. Consider treatment with topical corticosteroids and/or other symptomatic therapy (e.g., antihistamines).
Dermatologic event, Grade 2	 Continue atezolizumab. Consider patient referral to dermatologist. Initiate treatment with topical corticosteroids. Consider treatment with higher-potency topical corticosteroids if event does not improve.
Dermatologic event, Grade 3	 Withhold atezolizumab for up to 12 weeks after event onset. ^a Refer patient to dermatologist. Initiate treatment with corticosteroids equivalent to 10 mg/day oral prednisone, increasing dose to 1–2 mg/kg/day if event does not improve within 48–72 hours. If event resolves to Grade 1 or better, resume atezolizumab. ^b If event does not resolve to Grade 1 or better while withholding atezolizumab, permanently discontinue atezolizumab and contact Medical Monitor. ^c
Dermatologic event, Grade 4	 Permanently discontinue atezolizumab and contact Medical Monitor.^c

Table 9 Management Guidelines for Dermatologic Events

 ^a Atezolizumab may be withheld for a longer period of time (i.e., > 12 weeks after event onset) to allow for corticosteroids (if initiated) to be reduced to the equivalent of ≤10 mg/day oral prednisone. The acceptable length of the extended period of time must be agreed upon by the investigator and the Medical Monitor.

- ^b If corticosteroids have been initiated, they must be tapered over ≥ 1 month to the equivalent of ≤ 10 mg/day oral prednisone before atezolizumab can be resumed.
- ^c Resumption of atezolizumab may be considered in patients who are deriving benefit and have fully recovered from the immune-mediated event. Patients can be rechallenged with atezolizumab only after approval has been documented by both the investigator (or an appropriate delegate) and the Medical Monitor.

NEUROLOGIC DISORDERS

Myasthenia gravis and Guillain-Barré syndrome have been observed with single-agent atezolizumab. Patients may present with signs and symptoms of sensory and/or motor neuropathy. Diagnostic workup is essential for an accurate characterization to differentiate between alternative etiologies. Management guidelines for neurologic disorders are provided in Table 10.

Event	Management
Immune- mediated neuropathy, Grade 1	Continue atezolizumab.Investigate etiology.
Immune- mediated neuropathy, Grade 2	 Withhold atezolizumab for up to 12 weeks after event onset. ^a Investigate etiology. Initiate treatment as per institutional guidelines. If event resolves to Grade 1 or better, resume atezolizumab. ^b If event does not resolve to Grade 1 or better while withholding atezolizumab, permanently discontinue atezolizumab and contact Medical Monitor. ^c
Immune- mediated neuropathy, Grade 3 or 4	 Permanently discontinue atezolizumab and contact Medical Monitor.^c Initiate treatment as per institutional guidelines.
Myasthenia gravis and Guillain-Barré syndrome (any grade)	 Permanently discontinue atezolizumab and contact Medical Monitor. ^c Refer patient to neurologist. Initiate treatment as per institutional guidelines. Consider initiation of corticosteroids equivalent to 1–2 mg/kg/day oral or IV prednisone.

Table 10 Management Guidelines for Neurologic Disorders

^a Atezolizumab may be withheld for a longer period of time (i.e., > 12 weeks after event onset) to allow for corticosteroids (if initiated) to be reduced to the equivalent of ≤ 10 mg/day oral prednisone. The acceptable length of the extended period of time must be agreed upon by the investigator and the Medical Monitor.

- ^b If corticosteroids have been initiated, they must be tapered over ≥ 1 month to the equivalent of ≤ 10 mg/day oral prednisone before atezolizumab can be resumed.
- ^c Resumption of atezolizumab may be considered in patients who are deriving benefit and have fully recovered from the immune-mediated event. Patients can be rechallenged with atezolizumab only after approval has been documented by both the investigator (or an appropriate delegate) and the Medical Monitor.

IMMUNE-MEDIATED MENINGOENCEPHALITIS

Immune-mediated meningoencephalitis is an identified risk associated with the administration of atezolizumab. Immune-mediated meningoencephalitis should be suspected in any patient presenting with signs or symptoms suggestive of meningitis or encephalitis, including, but not limited to, headache, neck pain, confusion, seizure, motor or sensory dysfunction, and altered or depressed level of consciousness. Encephalopathy from metabolic or electrolyte imbalances needs to be distinguished from potential meningoencephalitis resulting from infection (bacterial, viral, or fungal) or progression of malignancy, or secondary to a paraneoplastic process.

All patients being considered for meningoencephalitis should be urgently evaluated with a CT scan and/or MRI scan of the brain to evaluate for metastasis, inflammation, or edema. If deemed safe by the treating physician, a lumbar puncture should be performed and a neurologist should be consulted.

Patients with signs and symptoms of meningoencephalitis, in the absence of an identified alternate etiology, should be treated according to the guidelines in Table 11.

Event	Management
Immune-mediated meningoencephalitis, all grades	 Permanently discontinue atezolizumab and contact Medical Monitor.^a Refer patient to neurologist.
	 Initiate treatment with corticosteroids equivalent to 1–2 mg/kg/day IV methylprednisolone and convert to 1–2 mg/kg/day oral prednisone or equivalent upon improvement.
	 If event does not improve within 48 hours after initiating corticosteroids, consider adding an immunosuppressive agent.
	 If event resolves to Grade 1 or better, taper corticosteroids over ≥ 1 month.

Table 11Management Guidelines for Immune-Mediated
Meningoencephalitis

^a Resumption of atezolizumab may be considered in patients who are deriving benefit and have fully recovered from the immune-mediated event. Patients can be re-challenged with atezolizumab only after approval has been documented by both the investigator (or an appropriate delegate) and the Medical Monitor.

RENAL EVENTS

Immune-mediated nephritis has been associated with the administration of atezolizumab. Eligible patients must have adequate renal function. Renal function, including serum creatinine, should be monitored throughout study treatment. Patients with abnormal renal function should be evaluated and treated for other more common

etiologies (including prerenal and postrenal causes, and concomitant medications such as non-steroidal anti-inflammatory drugs). Refer the patient to a renal specialist if clinically indicated. A renal biopsy may be required to enable a definitive diagnosis and appropriate treatment.

Patients with signs and symptoms of nephritis, in the absence of an identified alternate etiology, should be treated according to the guidelines in Table 12.

Event	Management
Renal event, Grade 1	 Continue atezolizumab. Monitor kidney function, including creatinine, closely until values resolve to within normal limits or to baseline values.
Renal event, Grade 2	 Withhold atezolizumab for up to 12 weeks after event onset. ^a Refer patient to renal specialist. Initiate treatment with corticosteroids equivalent to 1–2 mg/kg/day oral prednisone. If event resolves to Grade 1 or better, resume atezolizumab. ^b If event does not resolve to Grade 1 or better while withholding atezolizumab, permanently discontinue atezolizumab and contact Medical Monitor. ^c
Renal event, Grade 3 or 4	 Permanently discontinue atezolizumab and contact Medical Monitor. Refer patient to renal specialist and consider renal biopsy. Initiate treatment with corticosteroids equivalent to 1–2 mg/kg/day oral prednisone. If event does not improve within 48 hours after initiating corticosteroids, consider adding an immunosuppressive agent. If event resolves to Grade 1 or better, taper corticosteroids over ≥1 month.

Table 12 Management Guidelines for Renal Events

^a Atezolizumab may be withheld for a longer period of time (i.e., > 12 weeks after event onset) to allow for corticosteroids (if initiated) to be reduced to the equivalent of ≤ 10 mg/day oral prednisone. The acceptable length of the extended period of time must be agreed upon by the investigator and the Medical Monitor.

- ^b If corticosteroids have been initiated, they must be tapered over \geq 1 month to the equivalent of \leq 10 mg/day oral prednisone before atezolizumab can be resumed.
- ^c Resumption of atezolizumab may be considered in patients who are deriving benefit and have fully recovered from the immune-mediated event. Patients can be re-challenged with atezolizumab only after approval has been documented by both the investigator (or an appropriate delegate) and the Medical Monitor.

IMMUNE-MEDIATED MYOSITIS

Immune-mediated myositis has been associated with the administration of atezolizumab. Myositis or inflammatory myopathies are a group of disorders sharing the common feature of inflammatory muscle injury; dermatomyositis and polymyositis are among the most common disorders. Initial diagnosis is based on clinical (muscle weakness, muscle pain, skin rash in dermatomyositis), biochemical (serum creatine kinase increase), and imaging (electromyography/MRI) features, and is confirmed with a muscle biopsy.

Patients with signs and symptoms of myositis, in the absence of an identified alternate etiology, should be treated according to the guidelines in Table 13.

Event	Management
Immune- mediated myositis, Grade 1	Continue atezolizumab.Refer patient to rheumatologist or neurologist.Initiate treatment as per institutional guidelines.
Immune- mediated myositis, Grade 2	 Withhold atezolizumab for up to 12 weeks after event onset ^a and contact Medical Monitor. Refer patient to rheumatologist or neurologist. Initiate treatment as per institutional guidelines. Consider treatment with corticosteroids equivalent to 1–2 mg/kg/day IV methylprednisolone and convert to 1–2 mg/kg/day oral prednisone or equivalent upon improvement. If corticosteroids are initiated and event does not improve within 48 hours after initiating corticosteroids, consider adding an immunosuppressive agent. If event resolves to Grade 1 or better, resume atezolizumab. ^b If event does not resolve to Grade 1 or better while withholding atezolizumab, permanently discontinue atezolizumab and contact Medical Monitor. ^c

Table 13 Management Guidelines for Immune-Mediated Myositis

 ^a Atezolizumab may be withheld for a longer period of time (i.e., > 12 weeks after event onset) to allow for corticosteroids (if initiated) to be reduced to the equivalent of ≤ 10 mg/day oral prednisone. The acceptable length of the extended period of time must be agreed upon by the investigator and the Medical Monitor.

- ^b If corticosteroids have been initiated, they must be tapered over ≥ 1 month to the equivalent of ≤ 10 mg/day oral prednisone before atezolizumab can be resumed.
- ^c Resumption of atezolizumab may be considered in patients who are deriving benefit and have fully recovered from the immune-mediated event. Patients can be re-challenged with atezolizumab only after approval has been documented by both the investigator (or an appropriate delegate) and the Medical Monitor.

Table 13 Management Guidelines for Immune-Mediated Myositis (cont.)

Immune- mediated myositis, Grade 3	 Withhold atezolizumab for up to 12 weeks after event onset a and contact Medical Monitor. Refer patient to rheumatologist or neurologist. Initiate treatment as per institutional guidelines. Respiratory support may be required in more severe cases. Initiate treatment with corticosteroids equivalent to 1–2 mg/kg/day IV methylprednisolone, or higher-dose bolus if patient is severely compromised (e.g., cardiac or respiratory symptoms, dysphagia, or weakness that severely limits mobility); convert to 1–2 mg/kg/day oral prednisone or equivalent upon improvement. If event does not improve within 48 hours after initiating corticosteroids, consider adding an immunosuppressive agent. If event resolves to Grade 1 or better, resume atezolizumab. ^b If event does not resolve to Grade 1 or better while withholding atezolizumab, permanently discontinue atezolizumab and contact Medical Monitor. ^c
	 For recurrent events, treat as a Grade 4 event.
Immune- mediated myositis, Grade 4	 Permanently discontinue atezolizumab and contact Medical Monitor. ^c Refer patient to rheumatologist or neurologist. Initiate treatment as per institutional guidelines. Respiratory support may be required in more severe cases. Initiate treatment with corticosteroids equivalent to 1–2 mg/kg/day IV methylprednisolone, or higher-dose bolus if patient is severely compromised (e.g., cardiac or respiratory symptoms, dysphagia, or weakness that severely limits mobility); convert to 1–2 mg/kg/day oral prednisone or equivalent upon improvement. If event does not improve within 48 hours after initiating corticosteroids, consider adding an immunosuppressive agent. If event resolves to Grade 1 or better, taper corticosteroids over ≥ 1 month.

- ^a Atezolizumab may be withheld for a longer period of time (i.e., > 12 weeks after event onset) to allow for corticosteroids (if initiated) to be reduced to the equivalent of ≤10 mg/day oral prednisone. The acceptable length of the extended period of time must be agreed upon by the investigator and the Medical Monitor.
- ^b If corticosteroids have been initiated, they must be tapered over ≥ 1 month to the equivalent of ≤ 10 mg/day oral prednisone before atezolizumab can be resumed.
- ^c Resumption of atezolizumab may be considered in patients who are deriving benefit and have fully recovered from the immune-mediated event. Patients can be re-challenged with atezolizumab only after approval has been documented by both the investigator (or an appropriate delegate) and the Medical Monitor.

HEMOPHAGOCYTIC LYMPHOHISTIOCYTOSIS AND MACROPHAGE ACTIVATION SYNDROME

Immune-mediated reactions may involve any organ system and may lead to hemophagocytic lymphohistiocytosis (HLH) and macrophage activation syndrome (MAS).

Patients with suspected HLH should be diagnosed according to published criteria by McClain and Eckstein (2014). A patient should be classified as having HLH if five of the following eight criteria are met:

- Fever \geq 38.5°C
- Splenomegaly
- Peripheral blood cytopenia consisting of at least two of the following:
 - Hemoglobin < 90 g/L (9 g/dL) (< 100 g/L [10 g/dL] for infants < 4 weeks old)
 - Platelet count < 100×10^{9} /L (100,000/µL)
 - ANC < 1.0×10^9 /L (1000/µL)
- Fasting triglycerides > 2.992 mmol/L (265 mg/dL) and/or fibrinogen < 1.5 g/L (150 mg/dL)
- Hemophagocytosis in bone marrow, spleen, lymph node, or liver
- Low or absent natural killer cell activity
- Ferritin > 500 mg/L (500 ng/mL)
- Soluble interleukin 2 (IL-2) receptor (soluble CD25) elevated ≥2 standard deviations above age-adjusted laboratory-specific norms

Patients with suspected MAS should be diagnosed according to published criteria for systemic juvenile idiopathic arthritis by Ravelli et al. (2016). A febrile patient should be classified as having MAS if the following criteria are met:

- Ferritin > 684 mg/L (684 ng/mL)
- At least two of the following:
 - Platelet count \leq 181 × 10⁹/L (181,000/µL)
 - AST ≥48 U/L
 - Triglycerides > 1.761 mmol/L (156 mg/dL)
 - Fibrinogen \leq 3.6 g/L (360 mg/dL)

Patients with suspected HLH or MAS should be treated according to the guidelines in Table 14.

Table 14Management Guidelines for Suspected HemophagocyticLymphohistiocytosis or Macrophage Activation Syndrome

Event	Management
Suspected HLH or MAS	Permanently discontinue atezolizumab and contact Medical Monitor.Consider patient referral to hematologist.
	 Initiate supportive care, including intensive care monitoring if indicated per institutional guidelines.
	 Consider initiation of IV corticosteroids and/or an immunosuppressive agent.
	 If event does not improve within 48 hours after initiating corticosteroids, consider adding an immunosuppressive agent.

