5.1.4.2 Neutropenia

Neutropenia is an important identified risk for venetoclax. Clinical data from the oncology studies suggest that the neutropenia adverse events are observed among subjects who receive venetoclax as a single agent or in combination with other therapeutic agents, with higher frequency observed in some combination studies. Serious adverse events of neutropenia or neutropenia events that lead to discontinuations are few across the entire venetoclax oncology program. Neutropenia management guidelines are provided in Table 10 and Appendix 12. Granulocyte colony stimulating factors are permitted according to local practice, and patients will be monitored and treated promptly in case of infection.

Venetoclax—F. Hoffmann-La Roche Ltd Page 107 of 214 Protocol GO41864, Version 2

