Diarrhea should be controlled with adequate anti-diarrheal medication. Nausea and/or vomiting may be controlled with adequate anti-emetics. For Grade 3 or 4 neurotoxicity, chemotherapy should be resumed at 50% of the previous dose upon improvement or discontinued immediately (based on investigator's clinical judgment).

Suggested recommendations for dose modification of etoposide for renal impairment are provided in Table 9.

Table 9 Etoposide Dose Modification for Renal Impairment

Creatinine Clearance (mL/min)	Etoposide Dose	
> 50	100%	
15–50	75% of dose	

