5.1.6.3 Management of Potential Overlapping Toxicities

The main overlapping toxicities based on the individual safety profile of venetoclax and atezolizumab, carboplatin, and etoposide are expected to be hematologic toxicities such as neutropenia, febrile neutropenia, and thrombocytopenia (in the case of venetoclax, etoposide and carboplatin); and gastrointestinal toxicities such as diarrhea, nausea, and vomiting (in the case of venetoclax, atezolizumab, etoposide and carboplatin).

Table 10 below provides management guidelines for specific overlapping toxicities with venetoclax, atezolizumab and carboplatin etoposide. Nevertheless, the attribution and management of certain adverse events that have been associated with each agent separately (e.g., hepatotoxicity, skin and gastrointestinal toxicity) may be unclear when the agents are administered together. It is theoretically possible that allergic or inflammatory adverse events associated with carboplatin and etoposide (e.g., dermatitis, infusion-associated symptoms) could be exacerbated by the immunostimulatory activity of atezolizumab.

Toxicities should initially be managed according to the recommendations in Sections 5.1.5.1–5.1.5.3, Table 10, Appendix 12, and Appendix 13 with dose holds and modifications (if applicable) applied to the component of the study drug judged to be the primary cause. For severe (Grade 3) or persistent Grade 1–2 diarrhea, an endoscopic evaluation should be considered. Additional tests, such as autoimmune serology or biopsies, may be used to determine a possible immunogenic etiology for adverse events listed above. If, in the opinion of the investigator, atezolizumab is a potential inciting factor, the dose of atezolizumab may be held for a maximum of 105 days beyond the last infusion (see Section 5.1.5.2). Exceptions require Medical Monitor approval. Prompt symptomatic management is appropriate for mild immune-mediated adverse events. In severe cases, immune-mediated toxicities may be acutely managed with systemic corticosteroids or TNF- α inhibitors. These cases should be discussed with the Medical Monitor.

Table 10Management Guidelines for Specific Adverse Events with
Venetoclax, Atezolizumab, and Carboplatin Etoposide

Event	Management

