Event	Management
Non-hematologic Toxicity (Not specifically described in Table 9)	
Grade 3 or 4 non-hematologic events	 Delay venetoclax for a maximum of 28 days. First episode: If improvement to Grade ≤ 1 or baseline, resume previous doses of venetoclax. For subsequent episodes: If improvement to Grade ≤ 1 or baseline, restart venetoclax at one dose level reduction. Certain treatment-emergent non-hematologic adverse events (e.g., venous thromboembolic events) may be managed and become clinically stable following medical intervention but may not improve to Grade ≤ 1 according to the NCI CTCAE definitions. In such cases, if a patient is clinically stable, resumption of study drug may be possible after consultation with the Medical Monitor.
Grade 2 related non- hematologic toxicity	 Delay treatment with venetoclax until resolution to Grade ≤ 1 (or baseline status) for a maximum of 28 days. After resolution, resume full dose of venetoclax
Grade 1 non-hematologic toxicity	No dose reduction or delay.

Toxicities associated or possibly associated with atezolizumab treatment should be managed according to standard medical practice. Additional tests, such as autoimmune serology or biopsies, should be used to evaluate for a possible immunogenic etiology.

Although most immune-mediated adverse events observed with immunomodulatory agents have been mild and self-limiting, such events should be recognized early and treated promptly to avoid potential major complications. Discontinuation of atezolizumab may not have an immediate therapeutic effect, and in severe cases, immune-mediated toxicities may require acute management with topical corticosteroids, systemic corticosteroids, or other immunosuppressive agents.

The investigator should consider the benefit–risk balance a given patient may be experiencing prior to further administration of atezolizumab. In patients who have met the criteria for permanent discontinuation, resumption of atezolizumab may be considered if the patient is deriving benefit and has fully recovered from the immune-mediated event. Patients can be re-challenged with atezolizumab only after approval has been documented by both the investigator (or an appropriate delegate) and the Medical Monitor.

PULMONARY EVENTS

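### Appendix 12's venetoclax rule exempts toxicities in Table 9 where Table 10 is meant, leaving contradictory venetoclax instructions for hepatic events and diarrhea with no stated precedence

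*Combined protocol and SAP*

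**What the plan says.** Appendix 12 gives venetoclax rules by grade under the line "Non-hematologic Toxicity (Not specifically described in Table 9". For Grade 3 or 4 non-hematologic events venetoclax is held for at most 28 days. What follows depends on the episode. The initial one is handled thus: "First episode: If improvement to Grade ≤ 1 or baseline, resume previous doses of venetoclax". Any repeat that recovers to the same standard brings venetoclax back one level down.

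For related Grade 2 toxicity the instruction is: "Delay treatment with venetoclax until resolution to Grade ≤ 1 (or baseline status) for a maximum of 28 days". The full dose is then resumed.

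The document has two tables numbered 9. In Section 5.1.5.3 it is "Table 9 Etoposide Dose Modification for Renal Impairment". In Appendix 13 it is "Table 9 Management Guidelines for Dermatologic Events", which gives atezolizumab instructions only.

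Section 5.1.6.3 says: "Table 10 below provides management guidelines for specific overlapping toxicities with venetoclax, atezolizumab and carboplatin etoposide". That table has rows for Grade 3 and 4 diarrhea and for Grade 2, 3 and 4 hepatic events. Section 5.1.4.2 pairs it with the appendix: "Neutropenia management guidelines are provided in Table 10 and Appendix 12". Section 5.1.6.1 sends the reader to Appendix 12 alone for venetoclax-specific events. Section 5.1.6.3 lists Table 10 and Appendices 12 and 13 together and does not rank them.

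**The concern.** The scope line is the one piece of text that separates Appendix 12's general rule from the event-specific rules, and it names a table that describes no relevant event. Taken at its word it exempts neither hepatic events nor diarrhea, so both are covered twice. A site that goes to Appendix 12 through Section 5.1.6.1 finds a rule that looks complete and has no signal that another table says something different. The case that matters most is a Grade 4 hepatic event: one text resumes an investigational drug after recovery, the other stops it.

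**Working it through.** No sample size, power or error rate is involved. The check is to find what the scope line can mean and then compare the two texts event by event.

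**Step 1: which table is meant.** Body Table 9 (etoposide dose by creatinine clearance) contains no adverse event to exempt. Appendix 13 Table 9 (dermatologic events) has no venetoclax instruction. Table 8 governs chemotherapy, and its catch-all row for other Grade 3 or 4 toxicity would exempt every Grade 3 or 4 event and leave Appendix 12's Grade 3 or 4 rule empty. Table 10 in Section 5.1.6.3 lists specific events with venetoclax instructions and is cited with Appendix 12 in Sections 5.1.4.2 and 5.1.6.3. It is the only sensible target.

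**Step 2: venetoclax instruction after recovery, side by side.**

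| Event | Appendix 12 as written | Table 10 | Result |
|---|---|---|---|
| Hepatic, Grade 4 | First episode: previous dose. Later: one level lower. Hold of at most 28 days | Stop; no restart provision | Contradiction at any episode that recovers |
| Hepatic, Grade 3 | Same | One level lower | Contradiction at first episode only |
| Diarrhea, Grade 4, resolved | Same | One level lower | Contradiction at first episode only |
| Diarrhea, Grade 3, uncontrolled or hospitalized, once resolved | Same | One level lower | Contradiction at first episode only |
| Diarrhea, Grade 3, controlled | Same | Previous dose | Contradiction at later episodes only, opposite direction |
| Hepatic, Grade 2, related | Hold up to 28 days, then full dose | No venetoclax instruction | No contradiction; both can be followed |

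**Step 3: size in mg.** One level is read from Table 6 at the planned venetoclax doses: 800 to 600, 400 to 200, 200 to 100 mg.

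- First-episode contradictions, Appendix 12 minus Table 10: 800 − 600 = 200 mg; 400 − 200 = 200 mg; 200 − 100 = 100 mg.
- Later episodes of controlled Grade 3 diarrhea: 600 − 800 = −200 mg; 200 − 400 = −200 mg; 100 − 200 = −100 mg.
- Grade 4 hepatic event: the previous dose (one level lower at a later episode) against none.

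These are table steps, not an estimate of impact. The documents give no frequencies for these events.

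**Step 4: effect of correcting the reference.** With Table 10 exempted, every contradiction in Step 2 disappears.

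**Related slip.** Table 10's diarrhea rows cite Table 7, the chemotherapy table, for the venetoclax reduction in three places. This is clerical: Section 5.1.5.1 and Table 6 already define the venetoclax levels.

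**The case against.** A reader might infer that Appendix 12 overrides Table 10 and authorizes a restart after a Grade 4 hepatic event. The documents do not support that. The scope line limits Appendix 12 only; it does not switch Table 10 off, and Table 10 applies in its own right through Section 5.1.6.3. The result is two contradictory instructions, not an override. A careful reader would also prefer the event-specific row. That preference is reasonable, but the scope line is the text that should establish it, and it points elsewhere.

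The second argument is attribution. Section 5.1.6.3 applies holds to the drug judged the primary cause, and Appendix 12 is titled for events associated with venetoclax. Section 5.1.2 lists hepatotoxicity for etoposide and Section 5.1.1 immune-mediated hepatitis for atezolizumab, while Section 5.1.4 has no hepatic heading for venetoclax. This makes Appendix 12 a less likely route for a hepatic event. It does not settle precedence: Appendix 12's Grade 3 or 4 row, unlike its Grade 2 row, is not limited to related events.

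The third argument is the safeguards, and it largely stands as to risk. Section 3.3.2.3 requires Medical Monitor approval of dose modifications and supports reducing venetoclax for high-grade diarrhea, though it does not name hepatic events. Section 5.1.5 allows investigator discretion, and Section 5.1.5.1 sends unclear cases to the Medical Monitor. For a Grade 3 or 4 hepatic event, Appendix 13 Table 2 requires permanent discontinuation of atezolizumab and contact with the Medical Monitor. Grade 4 events are reported as serious (Table 11, footnote d) within 24 hours (Section 5.2.2), and hepatitis is an event of special interest (Section 5.2.3). None of these says which venetoclax rule governs.

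**Conclusion.** The cross-reference is wrong as written and leaves operative dosing text contradictory in five situations: Grade 4 hepatic events; first episodes of Grade 3 hepatic events, of resolved Grade 4 diarrhea, and of resolved uncontrolled or hospitalized Grade 3 diarrhea; and, in the opposite direction, later episodes of controlled Grade 3 diarrhea. Apart from the Grade 4 hepatic case, which is resume versus stop, the size is one Table 6 level. The conclusion assumes that Table 10 is the intended target, which Step 1 supports by elimination, and that the event recovers to the grade each rule requires, with Appendix 12's hold capped at 28 days.

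Practical risk is limited, for the reasons given above. Two further inferences should not be drawn. The related Grade 2 hepatic event is not a contradiction: Table 10 is silent on venetoclax there, and Appendix 12 adds a hold. Nor do the documents support an effect on DLT counts or the RP2D. Under Section 3.1.3, a related event requiring permanent discontinuation of any study drug is already a DLT, and a Grade 4 hepatic event discontinues atezolizumab whichever venetoclax rule is followed. The venetoclax restart dose is not a DLT criterion.

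**What to change.** In Appendix 12, replace the reference to Table 9 with Table 10 in Section 5.1.6.3; the section number is needed because Appendix 13 has its own Table 10 (neurologic disorders). Add one sentence: Table 10 governs wherever it gives a venetoclax instruction, and Appendix 12 applies otherwise. The second half matters. Giving Table 10 precedence for every event it lists would remove Appendix 12's hold for related Grade 2 hepatic events, on which Table 10 says nothing about venetoclax.

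As a clean-up, change the three venetoclax citations of Table 7 in Table 10's diarrhea rows to Table 6.

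The cost is amendment wording, with no operational burden. There is one small downside: repeated controlled Grade 3 diarrhea would follow Table 10's previous-dose rule, which is less conservative than Appendix 12's step down. If the sponsor prefers the step down, Table 10's Grade 3 diarrhea row should say so.
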